Short-term effects of gene-physical activity interaction on obesity and related metabolic indicators in children: a randomized controlled trial

1-February-2022

Research design

Ethics statement

This study was approved by the ethics committee of the China Medical University (Ethics Approval No. [2020] 075). Every participant signed an informed consent form. All methods were performed in accordance with the Declaration of Helsinki and relevant guidelines.

Study Design and Participants

This study is based on a randomized controlled trial of a 4-week MVPA intervention conducted among children aged 10-12 years with overweight or obesity problems. We followed the established criteria of overweight and obesity in Chinese children and adolescents proposed by the Working Group on Obesity in China (WGOC)¹⁴. Children with physical activity-limiting diseases and a lack of baseline or post-intervention physical examination data were excluded. Then a total of 139 children with overweight or obesity were randomly allocated (2:1) to MVPA intervention group (n=93) or a control group (n=46) after completing baseline measurement in June 2022.

Exercise program

The 4-week MVPA intervention engaged in supervised aerobic exercise, resistance training and interesting sport for 60 minutes, 3 days/week (Monday, Wednesday and Friday). Participants completed four sessions including preparation module (15 min), training module (30 min), and relaxation module (15 min). Another aerobic module (15 min) was added in each Friday. Children in intervention group

were also encouraged to take exercise for 10 minutes together with their parents at home two hours later after dinner including ten minutes' walking (at least 1000 meters) or at least 200 times rope skipping. Parents were invited to come to school at the beginning of the intervention program to accept project training. In order to safeguard the rights of the control groups, the same physical activity intervention was given to the control group at the end of the research.

Strength was measured by Tri-axial body motion recorder (ActiGraph, Wgt3x-BT, USA) to maintain relative intensity. Children were required to wear ActiGraph by a professional investigator on the left wrist, loosely tightened, and required to wear it at all times except for the shower during the intervention for 7 days. Valid data for each day were defined as: recording a wearing time of more than 8 hours, excluding sleep time, and recording counts per minute (CPM) of no more than 20 minutes of continuous 0 CPM. After the test, the raw data were analyzed using Actilife V6.13.4 software, and after extracting and calculating the daily average MET levels, CPMs per minute greater than 20,000 were excluded from the data, and the average daily total MVPA time was accumulated and calculated based on different physical activity intensity cut-offs (total MVPA time = total VPA time + total MPA time). The vector data recorded by the ActiGraph were transformed into different physical activity intensity times with cut-off points of 100 CBM for light physical activity, 2296 CPM for moderate intensity, and 4012 CPM for high-intensity activity, based on Evenson et al.'s ¹⁵ study about the proposed cut-off points.

At baseline, Physical Activity Questionnaire for Children (PAQ-C) was answered

by each participant. The PAQ-C reflects the overall physical activity level of children and adolescents in the past 7 days and the MVPA levels¹⁶. The scale consists of 10 items, 9 of which are structured to investigate MVPA levels in children and adolescents. A 1-5 scale was used to obtain a total score by summing the scores of the individual items. The PAQ-C scale scores < 2.33 defined as low physical activity levels, 2.33-3.66 as moderate physical activity levels, and >3.66 as high physical activity levels¹⁷.

Obesity outcomes

Height was measured to the nearest 0.1cm using Height Measuring Ruler (Selcom, Germany). Measurement was taken on the vertical distance from the apex of the skull to the ground in the standing position. Body weight and fat mass was measured to the nearest 0.1kg using Body Composition Analyzer (DC-13, Parade, Japan). Subjects were measured barefoot, wearing light. Waist circumference was measured to the nearest 0.1cm with circumference measuring tape. Measurement was taken between the lowest rib and the iliac crest with the abdomen relaxed at the end of a gentle expiration. Hip circumference was measured to the nearest 0.1cm with circumference measuring tape. Measurement was taken on the most prominent part of the buttocks and wraps it horizontally around the buttocks.

Preperitoneal fat and abdominal subcutaneous fat thickness were measured by ultrasonography. The thickness and area of preperitoneal fat and abdominal subcutaneous fat were measured with a linear array probe L12-5 (38 mm, 5-12 HZ) according to the method of Suzuki¹⁸. The linear array probe was placed vertically in

the median position of the upper abdomen, and the probe was moved 1-5cm above the umbilicus to obtain an image that included the maximum preperitoneal fat thickness. The probe was then placed vertically in the abdominal white line to obtain a transverse image. The preperitoneal fat thickness is the maximum height in the triangle. Abdominal subcutaneous fat thickness is the height above the triangle.

Blood pressure was measured by medical sphygmomanometer for 3 times. The subjects were at rest for more than 15 minutes. The blood pressure was measured on the right arm in a seated position with the elbow, sphygmomanometer and heart at the same level. All subjects were fasted for more than 12 hours. 3 ml of non-anticoagulated blood and 2 ml of EDTA anticoagulated blood were collected. The same medical examiner examined before and after the intervention to ensure data comparability.

Genotyping

The whole genomic DNA of blood mononuclear cells was performed using a fully automated nucleic acid extractor (QIAGEN, QIAcube, Germany), the DNA extraction reagents were used in a magnetic bead method DNA extraction kit (QIAGEN, 51331, Germany), and the detailed steps were performed according to the reagent and instrument instructions. 14 SNP loci associated with obesity and BMI were reliably validated based on GWAS studies in large Asian populations^{19, 20}. Genome-wide typing of the 14 targeted SNP loci was performed using the MassARRAY® system (AgenaBioscience Inc., USA) based on MALDI-TOF mass spectrometry for typing each locus. Due to the differences in the contribution effect of

each allele to obesity or BMI, a weighted genetic risk score (WGRS) was used to assess the genetic susceptibility to obesity in this study, calculated as follows:

$$WGRS = (\beta_1 \times SNP_1 + \beta_2 \times SNP_2 + \dots + \beta_{14} \times SNP_{14}) \times (\text{total SNP allele points} / \text{sum of } \beta\text{-effect coefficients})$$

where β_n coefficient is the contribution of each effect locus to BMI and obesity found in the GWAS study.

Covariates

Children's gender, age, date of birth, ethnicity and household income were collected in questionnaires answered by children at baseline. Non-quantitative Food Frequency Questionnaires (FFQ) was used to collect information on the dietary frequency, including 24 types of daily dietary foods such as cereals, flour, meat from livestock, seafood, vegetables, milk, snacks, and beverages. Dietary pattern factor score was calculated for each participant and included as covariate²¹.

Statistical Analyses

Data from the questionnaires and physical examination data was entered using EPIDATA 3.0 software, with trained entry clerks double-entering independently. All analysis was processed using SPSS 20.0 software, and a two-sided *P* value of less than 0.05 indicated a statistical difference with a test level of $\alpha=0.05$.

Baseline participant characteristic differences between intervention groups were evaluated by independent t-tests for continuous variables and chi-squared (χ^2) tests for categorical variables. The three possible genotypic frequencies for each gene studied were evaluated by Chi-Squared tests and found to be in Hardy–Weinberg equilibrium.

Associations between WGRS and obesity outcomes were analyzed using generalized linear models. Generalized linear models (GLM) were established to analyze two main effects of interest (gene, MVPA) and one interaction (gene \times MVPA) on each obesity outcome. Change in obesity outcome served as dependent variables. Covariates included age, sex, ethnicity, and family income status. Estimated marginal means of gene \times MVPA interaction, adjusted by the covariates, are presented in figures.

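### Gene × MVPA is tested on every obesity outcome at an unadjusted 0.05 with no primary outcome: at an assumed correlation of 0.5, a 16% to 29% chance of some false-positive interaction for four to ten outcomes

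*Combined protocol and SAP*

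**What the plan says.** The title makes the interaction between genes and physical activity the question of the trial. The Statistical Analyses section states: "Generalized linear models (GLM) were established to analyze two main effects of interest (gene, MVPA) and one interaction". That sentence goes on to say that this is done for each obesity outcome, and the next one adds: "Change in obesity outcome served as dependent variables". The decision rule, set once for all analyses, is that a two-sided P "value of less than 0.05 indicated a statistical difference with a test level of" 0.05.

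The dependent variables are not enumerated in that section. The section headed Obesity outcomes describes these adiposity measures:

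- Weight and fat mass: "Body weight and fat mass was measured to the nearest 0.1kg using Body Composition Analyzer".
- Waist: "Waist circumference was measured to the nearest 0.1cm with circumference measuring tape".
- Hip: "Hip circumference was measured to the nearest 0.1cm with circumference measuring tape".
- Two fat thicknesses: "Preperitoneal fat and abdominal subcutaneous fat thickness were measured by ultrasonography".

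That makes six. The same section also describes height, the areas of the same two fat depots ("The thickness and area of preperitoneal fat and abdominal subcutaneous fat were measured with a linear array probe") and blood pressure. The documents nowhere name a primary outcome, rank the outcomes, adjust for multiplicity or call the analysis exploratory.

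**The concern.** One interaction test is run per outcome, and each has its own 5% false-positive risk. With nothing to say which outcome carries the titled question, one P value below 0.05 on any of them meets the plan's only stated criterion. If the trial then makes a single claim that genetic risk modifies the response to exercise, the error rate of that claim is the chance of at least one false positive across the set, not 5%.

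A reader could correct for this if every interaction P value were reported. The plan says that adjusted marginal means for the interaction will be shown in figures, but it neither lists the outcomes nor undertakes to report every interaction test. That leaves room to present one nominal result as the answer.

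**Working it through.** The plan gives no familywise error rate, power or sample-size figure, so there is nothing of its own to reproduce.

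**Inputs from the documents:** two-sided 0.05 per test (Statistical Analyses); one interaction test per outcome on change from baseline (Statistical Analyses); 93 and 46 children per arm (Study Design and Participants).

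**Assumptions:**

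- Gene means the single WGRS, giving one interaction test per outcome.
- All interaction nulls are true.
- The test statistics are jointly normal with a common correlation ρ, which the documents do not give. Values of 0, 0.5 and 0.9 are shown.
- The number of outcomes k is 4 (a low count, for example fat mass, waist and the two fat thicknesses), 6 (the adiposity measures listed above) or 10 (adding two fat areas and systolic and diastolic blood pressure).

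**Formula.** For independent tests, the chance of at least one false positive is 1 − 0.95^k:

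- k = 4: 1 − 0.8145 = 0.185
- k = 6: 1 − 0.7351 = 0.265
- k = 10: 1 − 0.5987 = 0.401

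For correlation ρ, with c = 1.960, it is

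1 − ∫ φ(u) [Φ((c − √ρ·u)/√(1−ρ)) − Φ((−c − √ρ·u)/√(1−ρ))]^k du,

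evaluated numerically.

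| Outcomes | ρ = 0 | ρ = 0.5 | ρ = 0.9 |
|---|---|---|---|
| 4 | 18.5% | 15.6% | 9.4% |
| 6 | 26.5% | 20.7% | 10.8% |
| 10 | 40.1% | 28.7% | 12.8% |

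**Check by simulation.** In 20,000 simulated trials with 93 and 46 children, six outcomes and a regression on arm, score and arm × score without covariates, the rate was 21.0% at ρ = 0.5 and 11.0% at ρ = 0.9.

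**With Holm across all interaction tests** (all nulls true, ρ = 0, 0.5, 0.9): six tests give 4.9%, 4.1% and 2.1%; ten give 4.9%, 3.9% and 1.7%.

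**Price in power.** Take MVPA as randomised arm, equal WGRS spread in both arms, and residual SD equal to outcome SD. The standard error of the slope difference, in outcome SD per SD of WGRS, is then √(1/93 + 1/46) = 0.1803. The difference detectable with 80% power (normal approximation) is:

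- Unadjusted 0.05: 0.1803 × (1.960 + 0.842) = 0.505
- Holm's first step, six tests (0.05/6): 0.1803 × (2.638 + 0.842) = 0.63
- Holm's first step, ten tests (0.05/10): 0.1803 × (2.807 + 0.842) = 0.66

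**The case against.** The strongest reply is that the plan sets a threshold per test and never says that any one significant outcome settles the titled question. Each outcome, read alone, keeps its nominal 5%. That is correct: the familywise figure matters when one overall claim is drawn from the set. But the title poses one overall question, and the plan names no outcome that would answer it, so the objection limits the point without removing it.

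A second reply is that both the count and the correlation are unknown. This stands in full. Six is a count made from the Obesity outcomes section, not a number the plan states; fewer outcomes may be modelled, and the section also contains fat areas and blood pressure. A reader might therefore take 21% as the error rate, or 26% as its ceiling. The documents support neither. The 26% is the independence value for six tests of one score; for ten outcomes the corresponding value is 40%, which is itself unrealistic when thickness and area of the same depots are both included. The interaction sentence also does not define gene. If the 14 SNPs were tested singly, there would be further tests.

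A third reply is that exploratory work needs no adjustment. The plan does not describe itself as exploratory; if that is the intention, saying so is part of the remedy.

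**Conclusion.** The concern holds as a range. With four to ten outcomes, the chance of at least one false-positive gene × MVPA interaction is 16% to 29% at an assumed correlation of 0.5, 9% to 13% at 0.9, and 19% to 40% if the outcomes were independent. Even the lowest of these is nearly twice 5%. The figures assume one WGRS interaction per outcome and all interaction nulls true; they leave out the main-effect tests.

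Two stronger inferences should be resisted. First, a reader might conclude that simply naming a primary outcome now would bring the error to 5%. That holds only if the choice is made without sight of the results. If the outcome with the smallest of six P values were named primary, it would be significant exactly when any of the six was, and the error would stay at 20.7% at correlation 0.5.

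Second, a reader might conclude that outcome data had already been seen. The text is in the past tense, reports the Hardy–Weinberg result, excludes children without post-intervention examination data, and describes allocation in June 2022 under a February 2022 date. This makes prior sight of outcomes a real possibility but does not establish it. The point should be fixed; it does not invalidate the trial.

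**What to change.** List every outcome modelled. State that gene in the interaction is the WGRS, if that is meant; if single SNPs are also tested, include those tests in the list. Apply Holm at two-sided 0.05 across all listed gene × MVPA interaction tests, and report every interaction estimate with its confidence interval and P value. This keeps the familywise interaction error at or below 5% for the listed tests.

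Only if it can be documented that no post-intervention outcome data have been seen, an equivalent alternative is one primary interaction test at 0.05, with the remaining interactions tested by Holm only if the primary is significant. The gate matters: a primary at 0.05 beside an ungated Holm family at 0.05 leaves 8.2% at correlation 0.5 and 9.7% under independence with six outcomes.

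If outcome data have been seen, say so, use Holm across all the tests and label the interaction results exploratory; new text cannot restore pre-specification.

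The cost is a short paragraph and an outcome list, with no added data. Some nominally significant interactions can no longer be claimed. At Holm's first and strictest step, the slope difference detectable with 80% power rises from about 0.50 to about 0.63 (six tests) or 0.66 (ten tests) outcome SD per SD of WGRS, under the assumptions given with that calculation; later Holm steps are less demanding. Under the gated alternative the primary test keeps 0.50, but no secondary interaction can be claimed if it fails.

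### The models for change state no variance structure, and with 2:1 allocation a single residual variance gives wrong standard errors for the arm and gene × arm effects if the arms differ in residual spread

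*Combined protocol and SAP*

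**What the plan says.** Under Study Design and Participants, 139 children were "randomly allocated (2:1) to MVPA intervention group (n=93) or a control group (n=46").

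Under Statistical Analyses, the plan states: "Generalized linear models (GLM) were established to analyze two main effects of interest (gene, MVPA) and one interaction", the interaction being gene × MVPA. The response is a change score: "Change in obesity outcome served as dependent variables". The adjustment set is given as "Covariates included age, sex, ethnicity, and family income status". Estimated marginal means for the interaction are to be shown in figures. The software is SPSS 20.0, and a two-sided P "value of less than 0.05 indicated a statistical difference with a test level of" 0.05.

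The section does not give the distribution, link or scale parameter of the models. It does not say whether standard errors are model-based or robust, and it plans no comparison of residual spread between arms. No SD of change, pooled or by arm, appears anywhere, and there is no sample-size or power calculation.

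**The concern.** A generalized linear model for a continuous outcome, fitted in the usual way, estimates one residual variance for all children. At equal allocation this does little harm to the comparison of arms, because the pooled and true variances of the difference coincide whatever the SD ratio. At 2:1 they do not. The pooled estimate is dominated by the larger arm, while the precision of the contrast depends most on the smaller one.

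Two features of the design make a more variable exercising arm plausible:

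- **Uneven dose.** Under Exercise program, intervention children "were also encouraged to take exercise for 10 minutes together with their parents at home", so the amount of exercise done can vary from child to child. Controls received the programme only after the research ended.
- **Response that the score does not capture.** Under Genotyping, "a weighted genetic risk score (WGRS) was used to assess the genetic susceptibility to obesity in this study", with weights taken from each locus's effect on BMI and obesity, not on response to exercise. Differences in response that do not follow those weights stay in the residual of the exercising arm.

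At stake are the standard errors, P values and plotted intervals for the arm effect and for the gene × arm effect, which is the title question of the trial.

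**Working it through.** **Inputs.** n₁ = 93 and n₀ = 46 (Study Design and Participants); two-sided α = 0.05 (Statistical Analyses). Assumed: control residual SD = 1 and intervention residual SD = r, with r from 0.8 to 1.5 in the main table. There is no figure in the plan to reproduce. The arm sizes agree with the stated allocation: 93 + 46 = 139 and 93/46 = 2.02.

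**Closed form, two-arm contrast.**

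- Pooled residual variance: s² = (92r² + 45)/137
- Variance the one-variance model reports: V_model = s²(1/93 + 1/46) = 0.03249 s²
- True variance: V_true = r²/93 + 1/46
- SE ratio: k = √(V_model/V_true)
- Actual type I error: P(|t₁₃₇| > 1.977k), treating the correctly scaled statistic as t on 137 df

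For r = 1.25: s² = (92 × 1.5625 + 45)/137 = 1.378; V_model = 0.0448; V_true = 0.0168 + 0.0217 = 0.0385; k = 1.078; threshold 1.977 × 1.078 = 2.131; type I error 3.5%. The width is equivalent to losing 1 − 0.0385/0.0448 = 14% of the sample.

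| r (intervention/control) | k | Type I error |
|---|---|---|
| 0.8 | 0.928 | 6.9% |
| 1.0 | 1.000 | 5.0% |
| 1.1 | 1.033 | 4.3% |
| 1.25 | 1.078 | 3.5% |
| 1.5 | 1.141 | 2.6% |

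**Equal allocation for comparison.** With n per arm, V_model = ((r² + 1)/2)(2/n) = (r² + 1)/n = V_true, so k = 1 for every r. The exposure comes from the 2:1 split.

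**Simulation of the full model.** This used arm, a continuous standard normal risk score, arm × score and four covariate columns, with 20,000 runs per setting. The last column uses HC3 robust standard errors.

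| r | One-variance type I error: arm / gene × arm | HC3: arm / gene × arm |
|---|---|---|
| 0.8 | 7.0% / 7.0% | 4.5% / 4.8% |
| 1.0 | 5.1% / 5.0% | 4.5% / 4.7% |
| 1.25 | 3.4% / 3.6% | 4.2% / 4.5% |
| 1.5 | 2.8% / 2.5% | 4.4% / 4.2% |

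The interaction behaves like the arm effect.

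**Does the interaction itself create unequal residuals?** Take no gene effect in controls and an interaction of d residual SDs per SD of the score. The total SD ratio is √(1 + d²): 1.02, 1.04, 1.12 and 1.28 for d = 0.2, 0.3, 0.5 and 0.8. Once a correctly specified interaction term is fitted, the residual SD ratio is 1.00 in every case.

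**Power.** A separate simulation (4,000 replicates, effect 0.55 control SD; not independently repeated) compared one pooled variance with arm-specific variances:

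- r = 1.25: 73% to 78% for arm, 71% to 75% for gene × arm
- r = 1.5: 59% to 70% for arm, 58% to 69% for gene × arm
- r = 1: 84.8% with pooled variance, 84.4% with arm-specific variances

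**The case against.** **One residual variance is inferred.** The plan does not say it will use one. That is correct, and the point is worded accordingly: the plan is silent and the default is a single variance. If something else was intended, the plan needs the same sentence.

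**The trial's hypothesis does not imply unequal residuals.** A reader might infer that a trial about differing response, titled "Short-term effects of gene-physical activity interaction on obesity and related metabolic indicators in children", must expect more residual spread among exercisers. The documents do not support this. The hypothesis concerns mean outcomes, and the gene-driven spread is carried by the fitted gene × MVPA term, as the working shows. Only other sources could reach the residual: uneven adherence, response outside the score, or a misspecified score. The documents quantify none of them.

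**The larger ratios need a lot of heterogeneity.** If individual response is independent of natural change, r = 1.25 needs an unexplained response SD of √(1.25² − 1) = 0.75 control SD, and r = 1.5 needs 1.12. Against a mean effect of 0.55 these are 1.4 and 2.0 times the effect. Under normality about 23% and 31% of children would respond in the opposite direction. A response SD of 0.46 gives r = 1.1, where the standard error is only 3% too wide. This stands, and it is why the point is minor.

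**The inflating case lacks a mechanism.** Type I error rises only if controls vary more than exercisers. Nothing in the design suggests that, so r = 0.8 shows exposure and is not an expectation.

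What survives is that the plan neither allows for unequal spread nor checks for it, under an allocation that makes the standard errors sensitive to it.

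**Conclusion.** The point holds in conditional form. Under the default single residual variance and a 93 v 46 split, standard errors for arm and gene × arm are wrong if, and to the extent that, residual SDs differ by arm. If exercisers are the more variable group, which is plausible but undocumented, the tests are conservative and the cost is power. At r = 1.25 that is about 4 to 5 points in the simulated scenario. If controls are more variable, the level drifts up, to about 7% at r = 0.8. At equal SDs the default is correct.

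A reader might go further and conclude that the standard errors are likely wrong, or that the P values do not have their 5% level. Neither follows, because no SD by arm is given and the whole size of the effect rests on the assumed ratio. Nor does the plausible direction produce false positives.

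Severity is minor: a cheap improvement to the analysis section, not a defect that threatens the trial's conclusions.

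**What to change.** In Statistical Analyses, add a sentence such as: *Each model for change will be fitted with a separate residual variance for each arm and Satterthwaite degrees of freedom (SPSS MIXED). The arm effect, the gene × arm effect and the intervals on the estimated marginal means will be taken from this model.*

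Report the residual SD by arm beside the results, so that readers can see whether the allowance mattered.

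HC3 standard errors are a second choice. They kept type I error between 4.0% and 4.8% for SD ratios from 0.67 to 2.0, but in simulation they cost about 2 to 3 power points at equal variances and gained only about 2 at r = 1.25. The uncorrected sandwich estimator (HC0) should be avoided: with 46 controls it ran at 6–7% in simulation.

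**Cost.** One sentence and a different SPSS procedure, with no new data. If the variances are in fact equal, the loss is about 0.4 power points (84.8% to 84.4%) in the simulation quoted above.

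### The change-score models name no baseline value of the outcome as a covariate; adding it is a nearly free, low-priority gain in precision, not a repair of bias

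*Combined protocol and SAP*

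**What the plan says.** The Statistical Analyses section describes the model for each outcome: "Generalized linear models (GLM) were established to analyze two main effects of interest (gene, MVPA) and one interaction", namely gene × MVPA. It then says: "Change in obesity outcome served as dependent variables. Covariates included age, sex, ethnicity, and family income status". The Covariates section names one further variable: "Dietary pattern factor score was calculated for each participant and included as covariate". The baseline value of the outcome appears in neither list.

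That value is available. Under Study Design and Participants, children with "a lack of baseline or post-intervention physical examination data were excluded". Under Obesity outcomes, "The same medical examiner examined before and after the intervention to ensure data comparability". Randomisation was 2:1 after baseline measurement, with 93 intervention and 46 control children, 139 in all.

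The documents give no SD, pre/post correlation, effect size or power calculation.

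**The concern.** A change score is a regression on baseline with the slope fixed at 1. If the true slope differs, part of the baseline variation stays in the residual and widens the standard errors. A chance difference in baseline means between arms also carries through, in part, to the arm contrast.

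Gene × MVPA is the question in the trial's title, the control arm has only 46 children, and no power is stated. Precision that can be had from a variable already measured is therefore worth considering. Its value depends on the outcome: weight, fat mass, waist and hip probably track closely over 4 weeks, while blood pressure and ultrasound fat thickness may be noisier.

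**Working it through.** **Inputs.** From the documents: N = 139, arms 93 and 46 (93 + 46 = 139), the change score as dependent variable, and the covariate lists. Assumed: pre/post correlation r from 0.5 to 0.99, and ratio k of follow-up SD to baseline SD from 0.9 to 1.1. The plan states no figure that could be reproduced.

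**Variance formulas.** Set the baseline SD to 1 and the follow-up SD to k, with the same slope rk in both arms.

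- Change score: 1 + k² − 2rk.
- Adjusted for baseline: k²(1 − r²).
- Difference: (1 − rk)², which is never negative and is zero only when the slope rk equals 1.
- Price of estimating one more coefficient: 1 + 1/(N − p − 2). With p = 4 this is 1 + 1/133 = 1.0075; with p = 12 it is 1 + 1/125 = 1.0080.

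**Equal SDs (k = 1).** The ratio reduces to (1 + r)/2. Multiplied by 1.0075:

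| r | ratio before df cost | net ratio | 139 / net ratio (equivalent children) |
|---|---|---|---|
| 0.5 | 0.75 | 0.756 | 184.0 |
| 0.7 | 0.85 | 0.856 | 162.3 |
| 0.9 | 0.95 | 0.957 | 145.2 |
| 0.95 | 0.975 | 0.982 | 141.5 |
| 0.98 | 0.99 | 0.997 | 139.4 |

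Break-even is near r = 0.985. At r = 0.99 the net ratio is 0.995 × 1.0075 = 1.002.

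**Unequal SDs.**

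- r = 0.9, k = 0.9: 0.81 × 0.19 / 0.19 = 0.81, net 0.816.
- r = 0.9, k = 1.1: 1.21 × 0.19 / 0.23 = 1.00, net 1.01.
- r = 0.99, k = 0.9: 0.81 × 0.0199 / 0.028 = 0.576, net 0.58.

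For k between 0.9 and 1.1 the net ratio therefore runs from about 0.58 to 1.01.

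**Selection on overweight.** Suppose, as an extreme case, that the outcome itself is cut to the top 10–40% of a normal population. The ratio before the df cost is then 0.91–0.95 at population r = 0.5, 0.95–0.97 at 0.7 and 0.98–0.99 at 0.9. After the df cost, the gain at r ≥ 0.9 is about 0–1%.

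**Bias check.** A simulation used 93/46 children, 6,000 runs per r, a gene–baseline correlation of 0.3, a true arm effect of −0.10 and a true gene × arm effect of 0.05. Over r = 0.5 to 0.98 the change-score model gave arm estimates of −0.098 to −0.101, gene × arm estimates of 0.050 to 0.052 and type I error of 4.7–5.7%. With baseline added, the estimates covered the same ranges and type I error was 4.6–5.5%. At r = 0.9 the SE fell by 2.4% for arm and 2.3% for gene × arm.

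**Chance imbalance.** One SE of the baseline mean difference is √(1/93 + 1/46) = 0.180 SD. It moves the unadjusted arm contrast by −√((1 − r)/2) of its own SE: −0.50 at r = 0.5, −0.22 at 0.9 and −0.10 at 0.98. It does not move gene × arm. Only a chance arm difference in the gene–baseline slope does that.

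**Gene main effect.** Gene is not randomised, so adjustment changes what this coefficient estimates. With an assumed gene–baseline correlation of 0.3 and no gene effect on change given baseline, the unadjusted coefficient is (r − 1) × 0.3, which is −0.15 SD at r = 0.5 and −0.03 SD at r = 0.9. The adjusted coefficient is 0.

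**The case against.** **The gain may be nil where it matters most.** Close tracking over 4 weeks, together with selection on overweight, can leave weight-type outcomes with no measurable gain. This stands, and it is why the point is low priority.

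**No single percentage can be read from the documents.** This also stands. A figure such as 0–5% for weight-type outcomes needs r of at least 0.9 and nearly equal SDs, and neither is stated.

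**One pooled slope can lose precision under 2:1 allocation when the arms' slopes differ.** True. With assumed intervention/control slopes of 0.8/1.0, simulated variance ratios were 1.01 (arm) and 1.02 (gene × arm); with 0.7/1.1 both were 1.09. An arm × baseline term would address this, but where slopes are equal it costs about 1% on the interaction. It also adds a modelling choice, so it is not a sensible default.

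**The covariate list is not complete.** The dietary score appears in one section and not in the other, so absence from the list does not prove that baseline was left out of the fitted model. What can be said is that the documents do not name it.

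**The stronger reading.** A reader might infer that a change-score analysis without baseline is biased, or that regression to the mean in children selected for overweight produces a false intervention effect. The documents do not support that. Randomisation gives both arms the same expected regression to the mean, and the bias check above shows no distortion. This assurance covers randomised contrasts only. It would not apply if 'MVPA' means the measured time in the Exercise program section, where "the average daily total MVPA time was accumulated and calculated". Nor does it settle whether excluding children without post-intervention data disturbed the comparison. Both are separate points, and baseline adjustment would not reliably repair the second.

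**Conclusion.** The point holds as a free improvement of low priority. The documents name no baseline outcome covariate, although the data exist. If 'MVPA' is the randomised arm, and leaving aside the exclusion of children without post-intervention data, the omission costs precision and not validity for the arm and gene × arm estimates.

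Under assumed equal SDs and a common slope, the net variance reduction is about 24%, 14%, 4% and near 0 at r = 0.5, 0.7, 0.9 and 0.98. It is about zero at r ≥ 0.9 if selection truncates the outcome, larger if the follow-up SD is below the baseline SD, and at worst a loss of about 1%. None of these values of r or k comes from the documents.

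**What to change.** In the Statistical Analyses section:

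- Add the mean-centred baseline value of the outcome as one covariate in each model of change.
- Centre the WGRS if it enters as a continuous score. The documents mention no centring, and without it the arm coefficient is the effect at a score of zero.
- Report the arm and gene × arm estimates from that single model, with no arm × baseline term by default.
- Report the gene main effect also without baseline adjustment.
- The section is in the past tense. If the analysis is already done, label the adjusted model post hoc and show it beside the model now described.

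The cost is a few sentences, one degree of freedom per model and one further fit per outcome for the gene main effect. The named software can do this, and no new data are needed.
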